11.7 Left Ventricular Ejection Fraction (LVEF)

The Left ventricular ejection fraction (LVEF) are collected over time at selected visits. It will be measured by either echocardiography (ECHO) or MRI. Recorded values of LVEF and change from baseline values will be summarized by treatment group and by visit.

Corresponding listing will be provided for LVEF.

11.8 Antidrug Antibody Testing

The anti-drug antibody (ADA) binding to luspatercept (anti-ACE-536) will be tested over time in all subjects. The ADA level in samples confirmed positive to anti-ACE-536 will be semi-quantitated and reported as titer. Specificity tests and neutralizing ADA tests will be conducted only for samples confirmed positive to anti-ACE-536.

To evaluate the treatment-emergent ADA level, the number and percentage of the subjects for each ADA test will be presented by treatment group and ADA status. The ADA status of a subject during treatment is determined based on the longitudinal anti-ACE-536 results as following:

- Negative: All samples (baseline and post-baseline) are negative.
- Positive to treatment-emergent ADA:
 - At least one post-baseline sample is positive if the baseline sample is negative, or
 - At least one post-baseline sample is positive with a titer \geq 4-fold of the baseline titer if the baseline sample is positive
- Positive to preexisting ADA:
 - Baseline sample is positive and all post-baseline samples are negative, or
 - Both baseline and post-baseline samples are positive, but all positive post-baseline sample have a titer $<$ 4-fold of the baseline titer.

A separate table will summarize the number and percentage of the subjects and median (min, max) titer for anti-ACE-536 by treatment group, visit, and ADA status. In this table, only subjects tested positive to anti-ACE-536 will be included, and only positive subjects in the luspatercept arm will be summarized by ADA status. Corresponding listing will be provided to support the table.

Additionally, a bar plot will be provided for subject's ADA status ("Preexisting", "Treatment-Emergent" and "Negative"). Percent of subjects within each category will be displayed by treatment group.

11.9 Pregnancy Test and Menstrual Status for Female Subjects

The number and percentage of the subjects for each pregnancy test result category (i.e., positive, negative) will be presented by treatment group. A subject is counted as 'positive' if there is any positive result captured after first dose date, a subject is counted as 'negative' if there is no positive result captured after first dose date.

The pregnancy test along with menstrual status will be provided in a listing.

14 HEALTH RELATED QUALITY OF LIFE ANALYSIS

The HRQoL analyses are addressed in corresponding subsection in Section 10.4. This SAP only provides description of main HRQoL analysis specify in the protocol. A detailed statistical analysis of HRQoL data will be provided in a separate HRQoL SAP, which will be finalized prior to database lock. The HRQoL SAP will be appended to separate specific HRQoL report.

15 GENERAL INFORMATION

15.1 Interim Analysis

There is no interim analysis planned for this study.

15.2 DMC

The independent DMC will be composed of experts in the β -thalassemia not involved in ACE-536-B-THAL-002 protocol, an Independent Cardiologist, an Independent Statistician, and may include additional ad hoc members. Representatives of Sponsor will be attending the blinded part of the DMC meetings. The Sponsor will not have access to the unblinded data.

During the course of the study, the DMC will review unblinded safety data regularly, or ad-hoc, as well as safety and efficacy data in accordance with the guidelines for the preplanned analyses.

An independent third party will prepare the reports of aggregate data summaries and individual subject data listings, as appropriate, to the DMC members for each scheduled or ad-hoc meeting.

The DMC responsibilities, authorities, and procedures will be detailed in the DMC charter, which will be endorsed by the DMC prior to the first data review meeting.

Operational details for the DMC and the algorithm will be detailed in the DMC charter.

16 IMPACT OF COVID-19 ON EFFICACY AND SAFETY ANALYSIS

The outbreak of a respiratory disease caused by a novel coronavirus has quickly become a global pandemic. The virus has been named “SARS-CoV-2” and the disease it causes has been named “Coronavirus Disease 2019” (COVID-19). When the pandemic started, the study has finished enrollment of all patients and is on the way to collect the clinical data for the last 6 months.

The COVID-19 pandemic may impact the conduct and statistical analysis of clinical trials in 3 different aspects ([REDACTED])

1. Indirect (operational) impact – quarantine/travel restrictions, site closure, interruption of supply chain to investigational product, overwhelmed healthcare systems, enrollment slow/pause.
2. Direct impact on trial participants - COVID-19 infection, treatment for COVID-19.
3. Impact that may affect endpoint interpretation - delayed/missed visits/assessments, treatment delayed/interrupted/discontinued, study withdrawal, alternative ways of treatment administration, alternative ways of data collection.

Any subjects who had any pandemic-related scenarios mentioned above will be defined as the COVID-19-impacted population in the pandemic period. Any subjects who had contracted COVID-19 will be grouped as the COVID-19-infected population. Therefore, the COVID19-infected population is a subgroup of the COVID19-impacted population. The identification of the COVID-19-impacted and COVID-19-infected patients will be conducted on a weekly base and will be finalized prior to the database lock.

COVID-19 information for the COVID-19-impacted population will be captured in tables of subject disposition, concomitant medication, healthcare resource utilization, summary of dose delay, and protocol deviation. All these 5 tables will have the COVID-19-related fields. The subject disposition and dose delay tables provide the cause of discontinuation due to COVID-19. The protocol deviation table have sections specifying whether the deviations were caused by COVID-19. The table of concomitant medication captures COVID-19 medication if a subject is infected. The healthcare resource utilization table includes the reason for hospitalization caused by COVID-19.

16.1 Sensitivity Analysis of COVID-19 Impact on Efficacy Endpoints

The sensitivity analyses may be conducted for the primary and key secondary efficacy endpoints of the non-COVID-19-impacted patients by removing the COVID-19-impacted population to evaluate the effects of dose delays, missed central lab measurements, missed assessments, COVID-19 infection, or early discontinuation due to COVID-19.

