4.4. Sample Size Determination

Based on the assumption of targeted primary endpoint response rates of at least 50% in the luspatercept group and 10% for the placebo group, and 2:1 randomization, a total sample size of

150 (100 in the luspatercept group, 50 in the placebo group) will have at least 99% power to detect the difference between the 2 groups with a 2-sided alpha of 0.05 and assumed 10% dropout rate.

For NTDT-PRO T/W domain scores, assume the mean change from baseline scores at Week 24 are 1.2 and 0.5 for luspatercept and placebo group, respectively, with a common standard deviation of 1.2, the statistical power will be 91%.

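### The COVID-19 sensitivity analysis removes whole subjects whatever the endpoint window, so for the Week 13-24 endpoints it drops mostly pre-pandemic data and does not isolate a pandemic effect

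*SAP*

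**What the plan says.** SAP 16 describes the trial's stage at pandemic onset: "the study has finished enrollment of all patients and is on the way to collect the clinical data for the last 6 months". It lists operational effects, infection or its treatment, and effects on endpoint interpretation such as a delayed visit. It then sets the flag: "Any subjects who had any pandemic-related scenarios mentioned above will be defined as the COVID-19-impacted population in the pandemic period". The last words of that sentence date the event. They do not tie it to the interval over which an endpoint is measured.

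SAP 16.1 says that sensitivity analyses may be run on the primary and key secondary "efficacy endpoints of the non-COVID-19-impacted patients by removing the COVID-19-impacted population to evaluate the effects of dose delays", missed central laboratory values, missed assessments, infection and early discontinuation.

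The primary endpoint and key secondary endpoints 1 and 2 all use Weeks 13-24 (SAP 4.2). SAP 5.1 sets the haemoglobin interval at Days 86-169, with fallbacks of Days 79-162 and Days 93-176. Key secondary endpoint 3 uses Weeks 37-48 under the same rule. A missing responder status counts as non-response in the primary analysis, and missing continuous values are handled by complete case (SAP 10.6.1; 10.6.2 for NTDT-PRO).

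**The concern.** A dose delay or missed visit cannot alter an outcome whose window has already closed. Under the SAP 16 rule, one delayed visit in the pandemic still removes a subject from every analysis in 16.1, including endpoints that were complete months earlier. Subjects enrolled early stay in the double-blind period past their own Week 48, so an event after Week 48 would also remove a finished Week 37-48 outcome.

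Two consequences follow for Weeks 13-24. Valid data are discarded, so precision falls for a reason unrelated to the pandemic. Also, a subject who left the study before the pandemic cannot be flagged and is always kept. If that subject has no usable window data, the primary endpoint counts a non-responder, so non-responders of this kind gain weight as flagged subjects are removed. A weaker estimate or a lost p-value could then be reported as sensitivity to COVID-19.

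**Working it through.** **1. The plan's own power figures.** SAP 4.4 assumes "response rates of at least 50% in the luspatercept group and 10% for the placebo group", says that "150 (100 in the luspatercept group, 50 in the placebo group) will have at least 99% power" "with a 2-sided alpha of 0.05", and allows for an "assumed 10% dropout rate". The two-proportion calculation gives 0.9998 at 100/50 and 0.9995 at 90/45, so the figure reproduces. For T/W the SAP states "1.2 and 0.5 for luspatercept and placebo group, respectively, with a common standard deviation of 1.2, the statistical power will be 91" (percent). With difference 1.2 − 0.5 = 0.7 and SD 1.2, the noncentral t gives 91.7% at 100/50 and 88.7% at 90/45. The stated value lies between them, close to the figure without dropout.

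**2. Timeline (inferred from SAP 16).** Take 6 months as 6 × 30.4167 = 182.5 days, the conversion in SAP 18.1.1.

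- The last subject at onset was near Day 48 × 7 − 182.5 = 153.5, that is, Week 22.
- Share of that subject's window already past: (153.5 − 86 + 1)/84 = 82%.
- Anyone first dosed at least 169 − 153.5 = 15.5, so 16, days earlier had a complete window.

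The documents give no accrual period. Assuming uniform accrual over 6 to 24 months, 15.5/182.5 = 8.5% down to 15.5/730 = 2.1% of subjects had an open window at onset. The share of all window time before onset is 1 − 15.5²/(2 × 84 × A), where A is accrual in days. This exceeds 99% throughout the range. With 6.5 months remaining instead of 6, it is 97-99%.

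**3. Precision, continuous endpoints.** Under complete case, removing subjects at random leaves the expected mean difference unchanged. T/W power by noncentral t:

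| Subjects kept | Power |
|---|---|
| 100/50 | 91.7% |
| 60/30 | 73.2% |
| 50/25 | 65.2% |

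**4. Selection shift, primary endpoint.** Let d be the share who left the study before the pandemic without usable window data, equal in both arms, and i the share of the rest who are flagged. Assume full-ITT response of 50% and 10% and no pandemic effect.

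- Share kept: k = d + (1 − d)(1 − i).
- Response among those kept: 0.50(1 − i)/k and 0.10(1 − i)/k.
- Difference: 40(1 − i)/k points.

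The only attrition figure in the documents is 10% dropout. Spread evenly over 48 weeks, this gives 10% × 12/48 = 2.5% by Week 12 and 10% × 24/48 = 5% by Week 24. The flagged share i is an assumption.

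| d | i | k | Response | Difference |
|---|---|---|---|---|
| 0 | 50% | 0.500 | 50.0% v 10.0% | 40.0 |
| 2.5% | 50% | 0.5125 | 48.8% v 9.8% | 39.0 |
| 5% | 50% | 0.525 | 47.6% v 9.5% | 38.1 |
| 5% | 75% | 0.2875 | 43.5% v 8.7% | 34.8 |
| 10% | 50% | 0.550 | 45.5% v 9.1% | 36.4 |
| 10% | 75% | 0.325 | 38.5% v 7.7% | 30.8 |

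At d = 5% and i = 50%, power for the primary comparison is still about 96%, so loss of significance is unlikely under the planning assumptions.

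**5. Interval-specific flag.** With 12-month accrual, 15.5/365 = 4.2% of windows overlap the pandemic. At i = 50%, 2.1% are flagged. For d = 5%, k = 0.05 + 0.95 × 0.979 = 0.980, and the difference is 40 × 0.979/0.980 = 40.0 points, against 38.1 under the present rule.

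**The case against.** The analysis is optional and supportive. The confirmatory test is ITT with non-responder imputation, and the gatekeeping in SAP 10.1 uses only the main analyses. Missing haemoglobin already has several sensitivity analyses (SAP 10.2, 10.6.1), and T/W has imputation analyses (SAP 10.6.2). Any analysis that excludes subjects loses precision. The timeline rests on one loosely worded sentence. All of this stands, and it limits the consequence. It does not make the rule answer the question that 16.1 sets.

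A reader might infer three stronger claims, which the documents do not support.

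- *That three of the four tested endpoints are biased.* Non-responder imputation applies to binary outcomes only. For the two continuous Week 13-24 endpoints, leavers without data are already out, and the cost is mainly precision.
- *That all early discontinuers are kept.* Subjects who stop treatment enter follow-up with visits to Week 48 and beyond (Protocol 6.4), so they can be flagged for a missed visit. Only those who left the study before the pandemic are certain to be kept.
- *That the primary difference would fall by 5 points or more.* With half flagged, a fall to 34.8 needs d = 15%, which the documents do not support. Anyone who left after the window closed has an observed outcome. SAP 5.1 step d averages even one or two haemoglobin values, so early leavers are not all missing. A large shift would need more such leavers, or a much higher flagged share, than can be assumed.

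**Conclusion.** The concern holds in a limited form. SAP 16 and 16.1 remove subjects without regard to the endpoint window. On the inferred timeline, nearly all Week 13-24 data predate the pandemic, so for the primary endpoint and key secondary endpoints 1 and 2 the analysis drops mostly unaffected outcomes and does not isolate a pandemic effect.

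For the two continuous endpoints the cost is mainly precision. For the primary endpoint there is also a selection shift of about 1-2 points when 2.5-5% are pre-pandemic leavers without usable data and half of the rest are flagged. It grows with either share and vanishes with no such leavers. The documents give neither share, so these sizes illustrate and do not predict.

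For Weeks 37-48, some windows do overlap the pandemic and exclusion has more rationale. A reader should not conclude that the primary test, its alpha or the testing order is compromised. The point is worth correcting because the change is cheap and the result could otherwise be misread.

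**What to change.** In SAP 16.1, replace the single subject-level flag with one flag per endpoint interval:

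- **Weeks 13-24:** exclude a subject only if dosing or the relevant assessments were affected by the pandemic on or before the last day of the interval actually used. For haemoglobin this is Day 169, or Day 176 if the later fallback is used. The fallbacks are defined for haemoglobin only. For T/W, the Week 24 score ends on Day 24 × 7 = 168 (SAP 18.3.1).
- **Weeks 37-48:** apply the same rule at Day 169 + 168 = 337, or Day 176 + 168 = 344 for the corresponding fallback.
- **Everyone else:** keep all other ITT subjects, including those affected only after the interval closed.
- **Affected but valid assessments:** do not recode them as missing, because that could trigger non-responder imputation and create a new artefact.
- **Limit to state:** for Weeks 37-48 the exclusion still selects on remaining in the study, and the result should be read with that in mind.

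Report the number excluded per arm and interval, so that the loss of information is visible.

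The cost is a wording change and a date comparison for each subject and interval. SAP 16 already plans weekly identification of impacted subjects. The downside is two flags to maintain instead of one. No change to the main analysis or the sample size is needed.

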16.2 Analysis and Reporting of COVID-19 Impact on Safety Endpoints

The summary analyses for safety endpoints will be conducted on COVID-19-infected populations for any adverse events during the entire pandemic period.

Tables summarizing the incidence of TEAEs will be generated for each of the following by treatment group (if not otherwise specified, the summary is by SOC and PT) for COVID-19-infected populations:

- TEAEs;
- Serious TEAE (SAE);
- TEAE with CTCAE Grade ≥ 3 ;
- TEAEs leading to study drug discontinuation.

18 APPENDICES

18.1 Handling of Dates

Dates will be stored as numeric variables in the SAS analysis files and reported in DDMMYY format (ie, the Date9. datetime format in SAS). Dates in the clinical database are classified into the categories of procedure dates, log dates, milestone dates, and special dates.

- **Procedure Dates** are the dates on which given protocol-specified procedure are performed. They include the dates of laboratory testing, physical examinations, tumor scans, etc. They should be present whenever data for a protocol-specified procedure are present and should only be missing when a procedure is marked as NOT DONE in the database. Procedure dates will not be imputed.
- **Log Dates** are dates recorded in eCRF data logs. Specifically, they are the start and end dates for adverse events and concomitant medications/procedures. They should not be missing unless an event or medication is marked as *ongoing* in the database. Otherwise, incomplete log dates will be imputed according to the rules in Appendix 18.2 (eg, for duration or cycle assignment, etc.). However, in listings, log dates will be shown as recorded without imputation.
- **Milestone Dates** are dates of protocol milestones such as randomization, study drug start date, study drug termination date, study closure date, etc. They should not be missing if the milestone occurs for a subject. They will not be imputed.
- **Special Dates** cannot be classified in any of the above categories and they include the date of birth. They may be subject to variable-specific censoring and imputation rules.

Dates recorded in comment fields will not be imputed or reported in any specific format.

18.1.1 Calculation Using Dates

Calculations using dates (eg, subject's age or relative day after the first dose of study drug) will adhere to the following conventions:

- Study days after the start day of study drug will be calculated as the difference between the date of interest and the first date of dosing of study drug plus 1 day. The generalized calculation algorithm for relative day is the following:
 - If TARGET DATE \geq DSTART then STUDY DAY = (TARGET DATE – DSTART) + 1;
 - Else use STUDY DAY = TARGET DATE – DSTART.

Note that Study Day 1 is the first day of treatment of study drug. Negative study days are reflective of observations obtained during the baseline/screening period. Note: Partial dates for the first study drug are not imputed in general. All effort should be made to avoid incomplete study drug start dates.

- Age (expressed in years) is calculated: the number of months between birth date and informed consent date divided by 12 (if both dates are not missing), the integer part will be kept. If the month of birth date is the same as informed consent date and the day of birth date is greater than informed consent date, then the age calculated by above will minus 1. If any date is missing, AGE will be set to the age collected from CRF.
 - Partial birth date: impute missing day as 15th of the month; impute missing month as July; set missing age for missing year
- Intervals that are presented in weeks will be transformed from days to weeks by using (without truncation) the following conversion formula:

$$\text{WEEKS} = \text{DAYS} / 7$$

- Intervals that are presented in months will be transformed from days to months by using (without truncation) the following conversion formula:

$$\text{MONTHS} = \text{DAYS} / 30.4167$$

18.2 Date Imputation Guideline

18.2.1 Impute Missing Dates of Adverse Events/ Prior or Concomitant Medications, Procedures/Surgeries

Incomplete Start Date:

Missing day and month

- If the year is the **same** as the year of the first dosing date, then the day and month of the first dosing date will be assigned to the missing fields.
- If the year is **prior to** the year of first dosing date, then December 31 will be assigned to the missing fields.
- If the year is **after** the year of first dosing, then January 1 will be assigned to the missing fields.

Missing day only

- If the month and year are the **same** as the year and month of first dosing date, then the first dosing date will be assigned to the missing day.
- If either the year of the partial date is **before** the year of the first dosing date or the years of the partial date and the first dosing date are the same but the month of partial date is **before** the month of the first dosing date, then the last day of the month will be assigned to the missing day.
- If either the year of the partial date is **after** the year of the first dosing date or the years of the partial date and the first dose date are the same but the month of partial date is **after** the month of the first dosing date, then the first day of the month will be assigned to the missing day.

- If the stop date is not missing, and the imputed start date is after the stop date, the start date will be imputed by the stop date.

Missing day, month, and year

- No imputation is needed, the corresponding AE will be included as TEAE.

Incomplete Stop Date: If the imputed stop date is before the start date, then the imputed stop date will be equal to the start date.

Missing day and month

- If the year of the incomplete stop date is the **same** as the year of the last dosing date, then the day and month of the last dosing date will be assigned to the missing fields.
- If the year of the incomplete stop date is **prior to** the year of the last dosing date or prior to the year of the first dosing date, then December 31 will be assigned to the missing fields.
- If the year of the incomplete stop date is **prior to** the year of the last dosing date but is the same as the year of the first dosing date, then the first dosing date will be assigned to the missing date.
- If the year of the incomplete stop date is **after** the year of the last dosing date, then January 1 will be assigned to the missing fields.

Missing day only

- If the month and year of the incomplete stop date are the **same** as the month and year of the last dosing date, then the day of the last dosing date will be assigned to the missing day.
- If either the year of the partial date is **not equal to** the year of the last dosing date or the years of the partial date and the last dosing date are the same but the month of partial date is **not equal to** the month of the last dosing date, then the last day of the month will be assigned to the missing day.

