11.1 Adverse Events

Adverse events will be analyzed in terms of treatment-emergent adverse events (TEAEs) which are defined as any AEs that begin or worsen on or after the start of study drug through 63 days after the last dose of IP (i.e., AE start date on or after the first dose date and within last dose date + 63). In addition, an AE that occurs beyond this timeframe and that is assessed by the investigator as possibly related (suspected) to study drug will be considered as treatment-emergent.

All AEs will be coded using the Medical Dictionary for Regulatory Affairs® (MedDRA) dictionary. The incidence of TEAEs will be summarized by MedDRA system organ class (SOC) and preferred term (PT). The AE tables will be sorted by SOC and PT (within SOC) in descending frequency within the luspatercept group. If a subject experiences multiple AEs under the same PT (or SOC), then the subject will be counted only once for that PT (or SOC).

The intensity of AEs will be graded 1 to 5 according to the National Cancer Institute Common Terminology Criteria for Adverse Events (CTCAE) Version 4.0. If a subject experience the same AE more than once with different toxicity grades, then the event with the highest grade will be tabulated in “by grade” tables. In addition, AEs with a missing intensity will be presented in the summary table as an intensity category of “Missing” only if the same event category has no other valid grades.

Tables summarizing the incidence of TEAEs will be generated for each of the following by treatment group (if not otherwise specified, the summary is by SOC and PT):

- TEAEs;
- TEAEs by SOC only;
- Treatment-related TEAEs;
- Serious TEAE;
- Treatment-related serious TEAEs;
- TEAEs by CTCAE maximum severity
- Treatment-related TEAEs by CTCAE maximum severity
- TEAE with CTCAE Grade ≥ 3 ;

- Treatment-related TEAE with CTCAE Grade ≥ 3 ;
- TEAEs leading to study drug discontinuation;
- Treatment-related TEAEs leading to study drug discontinuation;
- TEAEs leading to study drug dose reduction;
- Treatment-related TEAEs leading to study drug dose reduction;
- TEAEs leading to death;
- Treatment-related TEAEs leading to death;
- Most frequent TEAEs by PT ($\geq 5\%$ in PT frequency of all subjects or subjects from any treatment group);
- Most frequent TEAEs by SOC ($\geq 5\%$ in SOC frequency of all subjects);
- Most frequent TEAEs by SOC and high level term (HLT) ($\geq 5\%$ in HLT frequency of all subjects);

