11.3 Other Adverse Events That Require Safety Analysis

Other adverse events that require safety analysis include AEs that fall under the “Embolic and Thrombotic Events and Thrombophlebitis” SMQ category and AEs with PT “Bone pain” and ‘Hypertension’.

Similar to AESI, summary will be provided for AEs that fall under the “Embolic and Thrombotic Events and Thrombophlebitis” SMQ category by preferred term. For “Bone pain” events, number of subjects with bone pain events by worst CTCAE grade will be provided from grade 1 to grade 5. The number and percentage of subjects with bone pain occurred during the first 24 weeks and after 24 weeks will be provided. Summary statistics will also be provided for time to first bone pain, total duration of bone pain (in days), total duration of bone pain that occurred during the first 24 weeks (in days), and total duration of bone pain that occurred after 24 weeks (in days). Total duration of bone pain is defined as sum of all bone pain duration within a subject, excluding overlapped period. Same summaries are also conducted on ‘Hypertension’.

The “Embolic and Thrombotic Events and Thrombophlebitis” SMQ category analysis will include subgroup analysis by splenectomy status, platelet above ULN, concomitant medications, and comorbidities as needed.

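### SAP 18.2.1: for a stop date with only a year, two imputation rules cover the same case, and one of them reduces an on-treatment adverse event to 1 day

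*SAP*

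**What the plan says.** SAP 18.2.1, under Incomplete Stop Date with day and month missing, gives four rules.

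- **Rule 1:** stop year equal to the last-dose year: use the day and month of the last dose.
- **Rule 2:** stop year before "the year of the last dosing date or prior to the year of the first dosing date, then December 31 will be assigned".
- **Rule 3:** stop year before the last-dose year "but is the same as the year of the first dosing date, then the first dosing date will be assigned to the missing date".
- **Rule 4:** stop year after the last-dose year: use January 1.

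A floor stands above all four: "If the imputed stop date is before the start date, then the imputed stop date will be equal to the start date".

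SAP 18.1 gives the purpose of these dates: "incomplete log dates will be imputed according to the rules in Appendix 18.2 (eg, for duration or cycle assignment, etc". The visible analysis that uses event duration is SAP 11.3: "Total duration of bone pain is defined as sum of all bone pain duration within a subject, excluding overlapped period". That section also splits the total at 24 weeks and plans the same summaries for hypertension.

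**The concern.** Rules 2 and 3 can both apply to one record and give different dates. Two programmers could each follow the SAP and produce different duration tables. The date in Rule 3 is also a poor choice for an on-treatment event. The first dosing date is the earliest possible on-treatment day, so any event that began later is given a stop before its start and is then cut to the minimum. The stake is an understated duration for bone pain and hypertension, which the SAP singles out for separate safety analysis.

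**Working it through.** **Which rules apply.** Write S for the stop year, F for the first-dose year and L for the last-dose year, with S known and day and month missing. Taking the four rules literally:

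| Year pattern | Rules met | Imputed stop |
|---|---|---|
| S < F | 2 | December 31 of S |
| S = F = L | 1 | last dosing date |
| S = F < L | 2 and 3 | December 31 of S, or first dosing date |
| F < S < L | 2 | December 31 of S |
| F < S = L | 1 | last dosing date |
| S > L | 4 | January 1 of S |

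Only S = F < L meets two rules; every other pattern meets exactly one. The rules for a missing day alone do not overlap.

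**What each rule does to duration.** SAP 11.3 does not define the duration of a single event. I assume stop − start + 1, the convention that SAP 10.4.13 uses for hemoglobin response. The dates are illustrative: first dose 15 Mar 2019, last dose 10 Feb 2020, bone pain starting 20 May 2019, stop recorded only as 2019.

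- Rule 2: stop = 31 Dec 2019. Days from 20 May to 31 Dec inclusive = 12 + 30 + 31 + 31 + 30 + 31 + 30 + 31 = **226 days**.
- Rule 3: stop = 15 Mar 2019, before the start. The floor moves it to 20 May 2019, so the duration is **1 day**.

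Without the +1 the figures are 225 and 0.

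The 1-day result does not depend on these dates. Under Rule 3 the stop is max(first dose, start), which equals the start for any event beginning on or after the first dose. If the start also has only the year of the first dose, the start rule applies, "then the day and month of the first dosing date will be assigned to the missing fields", and start and stop coincide again.

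**Comparison with Rule 1.** Keep the same event but let the last dose be 20 Dec 2019. Rule 1 then gives a stop of 20 Dec 2019, and 226 − 11 = 215 days. Under Rule 3, moving the last dose to 10 Feb 2020 cuts the same event from 215 days to 1.

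**How common the dosing pattern is.** SAP 10.4 places Week 48 at nominal Dose 17, and 16 intervals × 21 days = 336 days after Dose 1. If first doses are spread evenly over the year and no dose is delayed (both my assumptions), F < L holds for 336/365 = 92% of first-dose dates among subjects who reach Dose 17. This describes dosing calendars, not affected records.

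**The case against.** The best defence is that Rule 3 repeats Rule 2's trigger and adds a condition introduced by *but*, which is how a drafter writes a narrower exception. Read so, there is one outcome. That is a fair reading, though the SAP does not state it. It removes the ambiguity and leaves the collapse to 1 day. Reading *or* in Rule 2 as *and* would also remove the overlap, but would leave no rule for F < S < L.

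A second defence is that December 31 is no truer than the first dosing date: it replaces the shortest possible duration with the longest possible within that year, and Rule 4 shows that the SAP does not always impute late. That stands as a limit. December 31 is an upper bound, not an estimate. It does agree with the late imputation in Rule 1 and in the missing-day-only rules, which use the last dosing day or the end of the month.

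Third, Rule 3 may have been meant for entries that began before the first dose. With a first dose on 1 Mar 2019 and a start on 20 Feb 2019, Rule 3 gives 10 days and Rule 2 gives 315. Those entries do not collapse to 1 day, which is why the criticism is confined to events starting on or after the first dose.

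Fourth, such records should be few: SAP 18.1 expects log dates to be complete unless an entry is ongoing. This is accepted.

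**Conclusion.** The conflict is on the face of the SAP, and the 1-day result for on-treatment events survives the reading most favourable to the plan. It is a minor point. It needs a stop date lacking both day and month, a stop year equal to the first-dose year, and a last dose in a later year. The documents give no count of such records, so the effect on the bone pain and hypertension summaries cannot be sized. The 226-day and 1-day figures rest on invented dates and the +1 convention.

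A reader might infer more from this than the documents support:

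- **That 92% of subjects have wrong durations.** A subject is affected only with a year-only stop date in the first-dose year.
- **That safety incidence or efficacy shifts.** Treatment-emergent status rests on the start date ("AE start date on or after the first dose date and within last dose date + 63"), listings show dates as recorded, and no efficacy endpoint uses these dates.
- **That concomitant medication tables are distorted.** SAP 18.2.1 covers medications and procedures too, but no output whose result would change is visible.

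**What to change.** Make the rules mutually exclusive. Remove Rule 3 for events that start on or after the first dose, so that Rule 2's December 31 applies, and keep the floor. If Rule 3 is wanted for entries that began before the first dose, say so and exclude those entries from Rule 2. State that December 31 is an upper-bound convention.

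No cap at death or data cutoff is needed: December 31 of a year before the last-dose year always precedes the last dose, so such a cap could never bind.

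The cost is one edit to the SAP before database lock, with no new data. The small downside is that December 31 may overstate the duration of the few events concerned.
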